- have been treated with insulin 1 year preceding Visit 1 and between Visit 1 and Visit 3; or have been treated with any antihyperglycemic medication 90 days preceding Visit 1 and between Visit 1 and Visit 3

Note: An exception is for the use of insulin for gestational diabetes or short-term use (≤ 14 days) for certain clinical situations such as acute illness, hospitalization, or elective surgery

- have history of chronic or acute pancreatitis prior to Visit 1
- be currently requiring or receiving treatment for diabetic retinopathy and/or macular edema
- have been treated with prescription drugs or similar other body weight loss medications including over-the-counter (OTC) medications that promote weight loss within 90 days prior to Visit 1 and/or between Visit 1 and Visit 3
- have been receiving chronic (>2 weeks or 14 days) systemic glucocorticoid therapy (excluding topical, intraocular, intranasal, or inhaled preparations) or had received such therapy within 30 days of Visit 1 or between Visits 1 and 3.

Number of Participants:

[figure not shown]
Approximately 200 participants (50 participants per arm) will be randomized in a **CCI** ratio (tirzepatide 5 mg once weekly [QW], tirzepatide 10 mg QW, tirzepatide 15 mg QW, and placebo QW).

Ethical Considerations of Benefit/Risk:

Considering the data that are available to date from previous clinical studies, and the measures taken to ensure the safety of the participants in this study, the potential risks related with tirzepatide are justified by the anticipated benefits a participant with T2DM may experience in the study.

Data Monitoring Committee: No

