5.2. Exclusion Criteria

Participants are excluded from the study if any of the following criteria apply:

Medical Conditions

[8] Have T1DM

[9] Have a history of chronic or acute pancreatitis any time prior to study entry (Visit 1)

[10] Are currently requiring or receiving treatment for diabetic retinopathy and/or macular edema (e.g., laser photocoagulation or intravitreal injections of anti-vascular endothelial growth factor inhibitors). Must be verified by dilated fundoscopic examination performed by an ophthalmologist or optometrist if applicable within 90 days prior to Visit 1 or between Visit 2 and Visit 3.

Note: For participants with a contraindication to pharmacological pupil dilation (for example, closed angle glaucoma), a non-dilated fundoscopic examination performed by an ophthalmologist or optometrist is allowed.

[11] Have a history of ketoacidosis or hyperosmolar state/coma

[12] Have a known clinically significant gastric emptying abnormality (for example, severe diabetic gastroparesis or gastric outlet obstruction), have undergone or plan to have during the course of the study: gastric bypass (bariatric) surgery or restrictive bariatric surgery (for example, Lap-Band®), or chronically take drugs that directly affect gastrointestinal motility

[13] Have any of the following cardiovascular conditions within 60 days prior to Visit 1: acute myocardial infarction, cerebrovascular accident (stroke), or hospitalization due to congestive heart failure (CHF)

[14] Have a history of New York Heart Association Functional Classification IV CHF

[15] Have acute or chronic hepatitis including a history of autoimmune hepatitis, signs and symptoms of any other liver disease other than nonalcoholic fatty liver disease, or any of the following, as determined by the central laboratory at Visit 1:

- Alanine aminotransferase (ALT) or aspartate aminotransferase (AST) level ≥ 3.0 times the upper limit of normal (ULN) for the reference range
- Alkaline phosphatase (ALP) level $\geq 1.5 \times$ ULN for the reference range, or

- Total bilirubin (TBL) level $\geq 1.5 \times$ ULN for the reference range (except for cases of known Gilbert's Syndrome)
- Hepatitis B infection, defined as:
 - Positive hepatitis B core antibody and positive for hepatitis B virus DNA or
 - Positive hepatitis B surface antigen
- Positive hepatitis C antibody and positive hepatitis C virus RNA

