Note: Participants with nonalcoholic fatty liver disease are eligible to participate in this trial if their ALT level is $< 3.0 \times$ ULN for the reference range

- [16] Have an estimated glomerular filtration rate $< 30 \text{ mL/min/1.73 m}^2$, calculated by Chronic Kidney Disease-Epidemiology as determined by central laboratory at Visit 1
- [17] Have evidence of a significant, uncontrolled endocrine abnormality (for example, thyrotoxicosis or adrenal crises), in the opinion of the investigator
- [18] Have family or personal history of medullary thyroid carcinoma (MTC) or multiple endocrine neoplasia syndrome type 2 (MEN2)
- [19] Have a serum calcitonin level of $\geq 35 \text{ ng/L}$, as determined by central laboratory at Visit 1
- [20] Known or suspected hypersensitivity to trial product(s) or related products
- [21] Have evidence of a significant, active autoimmune abnormality (for example, lupus or rheumatoid arthritis) that, in the opinion of the investigator, is likely to require concurrent treatment with systemic glucocorticoids in the next 12 months
- [22] Have had a transplanted organ (corneal transplants [keratoplasty] allowed) or awaiting an organ transplant
- [23] Have a history of an active or untreated malignancy or are in remission from a clinically significant malignancy for less than 5 years. Exceptions for this criterion are:
 - basal or squamous cell skin cancer
 - *in situ* carcinomas of the cervix, and
 - *in situ* or grade 1 (for example, Gleason 6 or lower) prostate cancer
- [24] Have a history of any other condition (such as known drug, alcohol abuse, or psychiatric disorder) that, in the opinion of the investigator, may preclude the participant from following and completing the protocol
- [25] Have any hematological condition that may interfere with HbA1c measurement (for example, hemolytic anemias, sickle cell disease)

Prior/Concomitant Therapy

- [26] Use of insulin 1 year preceding Visit 1 and between Visit 1 and Visit 3; use of any antihyperglycemic medication 90 days preceding Visit 1 and between Visit 1 and Visit 3.

Note: An exception is for the use of insulin for gestational diabetes or short-term use (≤ 14 days) for certain clinical situations such as acute illness, hospitalization, or elective surgery.

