- [27] Have been treated with prescription drugs that promote weight loss (for example, Saxenda [liraglutide 3.0 mg], Wegovy [semaglutide 2.4mg], Xenical[®] [orlistat], Meridia[®] [sibutramine], Acutrim[®] [phenylpropanolamine], Sanorex[®] [mazindol], Adipex[®] [phentermine], BELVIQ[®] [lorcaserin], Qsymia[™] [phentermine/topiramate combination], Contrave[®] [naltrexone/bupropion], or similar other body weight loss medications including OTC medications [for example, alli[®]]) within 90 days prior to Visit 1 and/or between study entry (Visit 1) and randomization (Visit 3)
- [28] Are receiving chronic (>2 weeks or 14 days) systemic glucocorticoid therapy (excluding topical, intraocular, intranasal, or inhaled preparations) or have received such therapy within 30 days of Visit 1 or between Visits 1 and Visit 3

Prior/Concurrent Clinical Study Experience

- [29] Are currently enrolled in any other clinical study involving an investigational product or any other type of medical research judged not to be scientifically or medically compatible with this study
- [30] Have participated, within the last 30 days in a clinical study involving an investigational product. If the previous investigational product has 5 half-lives or 30 days (whichever is longer), should have passed prior to screening
- [31] Were previously enrolled and assigned to study intervention in this study, **received tirzepatide in any other study investigating tirzepatide**, or are currently taking or have used tirzepatide for any other reason outside of a clinical study

Other Exclusions

- [32] Are investigator site personnel directly affiliated with this study and/or their immediate families. Immediate family is defined as a spouse, parent, child, or sibling, whether biological or legally adopted
- [33] Are Lilly employees
- [34] Are unwilling or unable to comply with the use of a paper diary to directly record data from the participant.

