7.1. Discontinuation of Study Intervention

When necessary, a participant may be permanently discontinued from study intervention. If so, the participant will discontinue the study intervention, could receive another glucose-lowering intervention and will remain in the study and follow procedures for all remaining study visits, as shown in the SoA. The new glucose-lowering intervention will be recorded on the CRF specified for collecting antihyperglycemic medications.

A participant should be permanently discontinued from study intervention if

- the participant becomes pregnant during the study (will also be withdrawn from the study)
- the participant is diagnosed with T1DM (will also be withdrawn from the study)
- the participant discontinues due to a hepatic event or liver test abnormality (see section 7.1.1)
- the participant requests to discontinue study intervention.
- the participant is diagnosed with an acute or chronic pancreatitis
- the participant is diagnosed with MTC after randomization, or has post randomization calcitonin value ≥ 35 ng/L that has increased at least 50% over baseline
- the participant is diagnosed with an active or untreated malignancy (other than basal or squamous cell skin cancer, in situ carcinomas of the cervix, or in situ prostate cancer) after randomization
- the participant has any significant study intervention related hypersensitivity reaction
- the participant has any other TEAE, SAE, or clinically significant laboratory value for which the investigator believes that permanent study intervention discontinuation is the appropriate measure to be taken.

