- Alternate delivery of study intervention should be performed in a manner that does not compromise treatment blinding and ensures product integrity. The existing protocol requirements for product accountability remain unchanged, including verification of participant's receipt of study supplies.

- When delivering supplies to a location other than the study site (for example, participant's home), the investigator, sponsor, or both should ensure oversight of the shipping process to ensure accountability and product quality (that is, storage conditions maintained and intact packaging upon receipt).
- Instructions may be provided to the participant or designee on the final disposition of any unused or completed study supplies.

Screening period guidance

To ensure safety of study participants, laboratory values and other eligibility assessments taken at Visit 1 are valid for a maximum of 60 days. The following rules will be applied for active, nonrandomized participants whose participation in the study must be paused due to exceptional circumstances:

- If screening is paused for less than 60 days from Visit 1 to Visit 3: the participant will proceed to the next study visit per the usual SoA, provided that Visit 3 must be conducted within 60 days from Visit 1.
 - The site should conduct the next visit if the participant's eligibility criteria are confirmed, and the site should document the reason for delay.
 - Due to the pause in screening, sites should also reconfirm the impacted participant's consent and document this confirmation in the source documentation.
- If screening is paused for more than 60 days from Visit 1: The participant must be discontinued because of screening interruption due to an exceptional circumstance. This is documented as a screen failure in the CRF.

Adjustments to visit windows

Whenever possible and safe to do so, as determined by the investigator's discretion, participants should complete the usual SoA. To maximize the possibility that these visits can be conducted as on-site visits, the windows for visits may be adjusted, upon further guidance from the sponsor. This minimizes missing data and preserves the intended conduct of the study.

This table describes the allowed adjustments to visit windows.

| Visit Number | Tolerance |
|-------------------------|--|
| Visit 1 (Screening) | No change. |
| Visit 2 | At least 4 days before Visit 3. |
| Visit 3 (Randomization) | Within 60 days after Visit 1. |

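### The pancreatitis and recent cardiovascular exclusions close at Visit 1, so an event in the lead-in before randomisation at Visit 3 does not meet them

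*Protocol*

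**What the plan says.** All of the following is in the protocol.

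- **Criterion [9], Section 5.2:** "Have a history of chronic or acute pancreatitis any time prior to study entry (Visit 1". The synopsis has the same anchor: "have history of chronic or acute pancreatitis prior to Visit 1".
- **Criterion [13], Section 5.2:** "Have any of the following cardiovascular conditions within 60 days prior to Visit 1", followed by acute myocardial infarction, stroke and hospitalisation for congestive heart failure.
- **Criteria [26] to [28], Section 5.2:** each adds the lead-in. [26] has "use of any antihyperglycemic medication 90 days preceding Visit 1 and between Visit 1 and Visit 3", [27] has "within 90 days prior to Visit 1 and/or between study entry (Visit 1) and randomization (Visit 3" and [28] has "have received such therapy within 30 days of Visit 1 or between Visits 1 and Visit 3".
- **Sections 4.1 and 6.3:** people who satisfy the enrolment criteria are randomised at Visit 3 and take the first dose there.
- **Section 7.1:** the reasons for permanent discontinuation of study intervention include "the participant is diagnosed with an acute or chronic pancreatitis". The neighbouring items on medullary thyroid carcinoma and other malignancy are limited to the time after randomisation; the pancreatitis item is not.
- **Section 10.8 (Appendix 8):** when screening is paused by exceptional circumstances, "laboratory values and other eligibility assessments taken at Visit 1 are valid for a maximum of 60 days", and Visit 3 must fall within that time.

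**The concern.** An eligibility rule about recent or past events should normally look back from the point at which the participant is exposed. Here it looks back from consent and screening. The most recent interval before the first injection, which matters most for an acute event, is the one that [9] and [13] do not cover. For [13] this reverses the ordering: a more distant infarction excludes and a more recent one does not. For pancreatitis, the written rules would let a person be randomised with a diagnosis that Section 7.1 treats as a reason to stop permanently.

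Section 2.3.1 lists acute pancreatitis and increased pulse rate among the potential risks of tirzepatide, and Section 8.3.4 sends pancreatic and cardiovascular events to adjudication. Participant safety is therefore what is chiefly at stake.

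**Working it through.** The plan states no figure to reproduce. The check compares date windows and sets the passages side by side.

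**1. Windows.** Let L be the number of days from Visit 1 to Visit 3. Counting back from Visit 3:

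- [9] covers every event more than L days back and leaves the last L days open.
- [13] covers events from L to L + 60 days back and leaves the last L days open.
- An infarction 59 days before Visit 1 lies L + 59 days before Visit 3 and is excluded.
- An infarction the day after Visit 1 lies L − 1 days before Visit 3 and is not excluded.

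The routine value of L is redacted. The first two rows below are assumptions; the third is the Appendix 8 maximum.

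| L (days) | Days before Visit 3 covered by [13] | Days left open | Excluded example (L + 59) | Example not excluded (L − 1) |
|---|---|---|---|---|
| 7 | 7 to 67 | last 7 | 66 | 6 |
| 21 | 21 to 81 | last 21 | 80 | 20 |
| 60 | 60 to 120 | last 60 | 119 | 59 |

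The reversal holds for any L above 1 day. L sets the size of the gap, not its existence.

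**2. Does anything carry [9] or [13] forward?** No general clause in Section 5 does so. [11] (ketoacidosis or hyperosmolar state) and [14] (NYHA class IV heart failure) have no Visit 1 limit, so they still operate at Visit 3. The limit in [9] and [13] is therefore specific wording, not a convention applied to every history item.

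**3. Section 7.1 against [9].** If the pancreatitis item covers any diagnosis during the study, a lead-in case is eligible under [9] and already meets a reason for permanent discontinuation. If it covers only diagnoses made on treatment, nothing mandatory addresses the lead-in case. Either way, the two passages need to be reconciled.

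**4. Remaining safeguards.**

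- [24] rests on the investigator's opinion about whether the person can follow and complete the protocol.
- Withdrawal for safety reasons under Section 7.2 is permitted, not required.
- The Visit 3 ECG (Sections 1.3 and 4.1) may reveal a cardiac event, but no eligibility rule is tied to it.
- The Appendix 8 eligibility confirmation is made against the criteria as written.

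**5. Effect on the analysis.** SAP Table GPIU.4.1 starts the adverse-event baseline period at screening and ends it before the first dose. SAP Section 4.11.2 counts an event as treatment-emergent only if it first occurs or worsens after the first dose, judged by MedDRA Lowest Level Term (LLT) against the maximum baseline severity. A lead-in event that continues, or recurs under the same LLT at no greater severity, is not counted. One that worsens or is coded to a different LLT is counted. A missing post-baseline severity is treated as severe and can therefore register as worsening.

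**The case against.** The strongest reply is that a careful investigator would not randomise someone with a fresh infarction or pancreatitis, and that [24], Section 7.2 and the Visit 3 ECG give room to prevent it. That is fair as a forecast. A reader might infer from the criteria that such a person would certainly be randomised, or that sites will differ in whom they randomise; the documents establish neither. What stands is that prevention rests on judgement, although Section 5 does not allow waivers and so relies on the written criteria.

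A second reply is that [26] to [28] concern drugs that would confound baseline HbA1c and weight, so they do not show that the plan regards the lead-in as a risk period for medical events. This is right. They show only that the protocol has wording for extending a window to Visit 3 and uses it where it means to. Other criteria, such as [2], [4], [15], [16] and [19], are also tied to Visit 1, but they rest on measurements taken at that visit, whereas [9] and [13] are event histories that can change afterwards.

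A third reply is that the safety results are hardly exposed. This largely stands. A reader might infer that any recurrence of a lead-in event would inflate the adjudicated safety counts, since one case is 1/50 = 2% of an arm. The SAP does not support that. Its baseline rule removes most such events. Cardiovascular events are listed (Section 4.11.4.7), pancreatic summaries are conditional on the data (Section 4.11.4.3), events in fewer than 10 patients may be listed only, and safety p-values are not used for hypothesis testing (Section 4.11).

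Finally, a reader might take 60 days as the usual exposure. It is a ceiling for paused screening under Appendix 8 only.

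**Conclusion.** The gap in the written criteria is real. Between Visit 1 and Visit 3, a new pancreatitis does not meet [9], and a new infarction, stroke or heart-failure admission does not meet [13], although the same event before Visit 1 (for [13], within 60 days) would. For pancreatitis the wording also conflicts with Section 7.1. The gap lasts L days: unknown in routine conduct because of redaction, and at most 60 under Appendix 8.

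Events will be rare among about 200 participants. The consequence is mainly for participant safety; the effect on the trial's conclusions is small, and no efficacy or type 1 error result is touched. This rests on the literal wording of the criteria and on finding no clause that carries them forward. It takes no view on which clinical window is right.

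**What to change.** Reconcile the time anchors of [9], its synopsis version and [13] with randomisation at Visit 3, with the pattern in [26] to [28], and with Section 7.1. The criteria should state explicitly how an event between Visit 1 and Visit 3 affects eligibility; the sponsor sets the clinical window. Have sites check these items at Visit 3 before entry in the IWRS. Medical history is scheduled only at Visit 1, but adverse events are already collected at Visits 1, 2 and 3, so no new procedure is needed.

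The cost is a wording amendment, with the ethics approval (and health authority approval if substantial) that Section 10.1.1 requires, and at most a rare extra screen failure.

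The SAP version history merges two diabetes-duration subgroups because few participants fell in them, which suggests that enrolment was well advanced. If enrolment has closed, rewording the criteria changes nothing. Instead, identify any lead-in pancreatitis, infarction, stroke or heart-failure admission among randomised participants and report it alongside the adjudicated events.

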5.3. Lifestyle Considerations

Per the SoA (Section 1.3), qualified medical staff will provide diabetes management counseling, which will include instructions on diet and exercise and education about the signs, symptoms, and treatment of hypoglycemia, should it occur.

Participants should continue their usual exercise habits and generally follow a healthy meal plan (with consistent meal size and time of day) throughout the course of the study. Dietary counseling may be reviewed throughout the study, as needed. Per Inclusion Criterion [3]

(Section 5.1), participants should not initiate an organized diet and/or exercise (weight reduction) program during the study other than the lifestyle and dietary measures for diabetes treatment.

Study participants should be instructed not to donate blood or blood products during the study.

5.4. Screen Failures

A screen failure occurs when a participant who consents to participate in the clinical study is not subsequently assigned to study intervention. A minimal set of screen failure information is required to ensure transparent reporting of screen failure participants to meet the Consolidated Standards of Reporting Trials (CONSORT) publishing requirements and to respond to queries from regulatory authorities. Minimal information includes demography, screen failure details, eligibility criteria, and any SAE.

Individuals who do not meet the criteria for participation in this study (screen failure) must not be rescreened.

5.5. Criteria for Temporarily Delaying Enrollment/Randomization/Administration of Study Intervention of a Participant

Not applicable.

6. Study Intervention(s) and Concomitant Therapy

Study intervention is defined as any investigational intervention(s), marketed product(s), placebo, or medical device(s) intended to be administered to/used by a study participant according to the study protocol.

6.1. Study Intervention(s) Administered

Assignment to study intervention (tirzepatide 3 doses or placebo) will occur at randomization. Beginning at randomization, all participants will receive study intervention according to the randomized treatment group for the duration of the **CCI** treatment period. Following randomization, the participant will inject the first dose of study intervention at the study site. The date and time of study intervention should be recorded on the paper diary and transcribed to the CRF.

6.1.1. Study intervention

This table lists the interventions used in this clinical study.

| Intervention Name | Tirzepatide 5 mg | Tirzepatide 10 mg | Tirzepatide 15 mg | Placebo |
|--------------------------------|--------------------------|--|--|---------|
| Dosage Level(s) | 2.5 mg QW 5 mg QW | 2.5 mg QW 5 mg QW 7.5 mg 10 mg QW | 2.5 mg QW 5 mg QW 7.5 mg 10 mg QW 12.5 mg QW 15 mg QW | NA |
| Route of Administration | SC | | | |
| Use | Investigational compound | | | |
| Drug formulation | SDP | | | |

Abbreviations: NA=not applicable; QW=once weekly; SDP= single-dose pen; SC=subcutaneous.

Tirzepatide dosing

The starting dose of tirzepatide will be 2.5 mg QW for 4 weeks, followed by an increase to 5 mg QW, for the duration of the study for the 5-mg group.

For the 10-mg group, the starting dose of tirzepatide will be 2.5 mg QW for 4 weeks, then the dose will be increased by 2.5 mg every 4 weeks (2.5 mg to 5 mg to 7.5 mg to 10 mg) until the 10-mg dose is reached and maintained for the duration of the study.

For the 15-mg group, the starting dose of tirzepatide will be 2.5 mg QW for 4 weeks, then the dose will be increased by 2.5 mg every 4 weeks (2.5 mg to 5 mg to 7.5 mg to 10 mg to 12.5 mg to 15 mg) until the 15-mg dose is reached and maintained for the duration of the study.

Placebo dosing

Participants randomized to the placebo group will inject matched placebo QW for the entire treatment period.

Timing of doses of study intervention

There are no restrictions on the time of day each weekly dose of study intervention is given, but it is advisable to administer the subcutaneous injections on the same day and same time each week, with or without meals. The actual date and time of all dose administrations will be recorded by the participant. If a dose of study intervention is missed, the participant should take it as soon as possible unless it is within 72 hours of the next dose, in which case, that dose should be skipped and the next dose should be taken at the appropriate time. The day of weekly administration can be changed if necessary, as long as the last dose was administered 72 or more hours before.

All participants will inject study intervention subcutaneously in the abdomen or thigh using the injection supplies provided; a caregiver may administer the injection in the participant's upper arm. A new SDP will be used for each injection. If study intervention is to always be injected in the same body region, participants should be advised to use a different injection site each week.

Study intervention returning

Participants should return all study interventions to the site according to the SoA (Section 1.3). Participants should be instructed to discard all used SDPs in a closeable, puncture-resistant container according to local regulations.

Returned study intervention should not be re-dispensed to the participants.

Packaging and labeling

Study interventions will be supplied by the sponsor in accordance with current Good Manufacturing Practice. Study interventions will be labeled as appropriate for country requirements.

The sponsor will provide tirzepatide and placebo in SDP which will be packaged in cartons to be dispensed. Clinical study materials will be labeled according to the country's regulatory requirements.

